##### **8.4.1.1. Reporting SAEs to Pfizer Safety**

All SAEs occurring in a participant during the active collection period as described in Section 8.4.1 are reported to Pfizer Safety via PSSA immediately upon awareness and under no circumstance should this exceed 24 hours, as indicated in [Appendix 3](#). The investigator will submit any updated SAE data to the sponsor within 24 hours of its being available.

##### **8.4.1.2. Recording Nonserious AEs and SAEs on the CRF**

All nonserious AEs and SAEs occurring in a participant during the active collection period, which begins after obtaining informed consent as described in Section 8.4.1, will be recorded on the AE section of the CRF.

The investigator is to record on the CRF all directly observed and all spontaneously reported AEs and SAEs reported by the participant.

As part of ongoing safety reviews conducted by the sponsor, any nonserious AE that is determined by the sponsor to be serious will be reported by the sponsor as an SAE. To assist in the determination of case seriousness, further information may be requested from the investigator to provide clarity and understanding of the event in the context of the clinical study.

#### **8.4.2. Method of Detecting AEs and SAEs**

The method of recording, evaluating, and assessing causality of AEs and SAEs and the procedures for completing and transmitting SAE reports are provided in [Appendix 3](#).

Care will be taken not to introduce bias when detecting AEs and/or SAEs. Open-ended and nonleading verbal questioning of the participant is the preferred method to inquire about AE occurrences.

#### **8.4.3. Follow-Up of AEs and SAEs**

After the initial AE or SAE report, the investigator is required to proactively follow each participant at subsequent visits/contacts. For each event, the investigator must pursue and obtain adequate information until resolution, stabilization, the event is otherwise explained, or the participant is lost to follow-up (as defined in [Section 7.3](#)).

In general, follow-up information will include a description of the event in sufficient detail to allow for a complete medical assessment of the case and independent determination of possible causality. Any information relevant to the event, such as concomitant medications and illnesses, must be provided. In the case of a participant death, a summary of available autopsy findings must be submitted as soon as possible to Pfizer Safety.

Further information on follow-up procedures is provided in [Appendix 3](#).

#### **8.4.4. Regulatory Reporting Requirements for SAEs**

Prompt notification by the investigator to the sponsor of an SAE is essential so that legal obligations and ethical responsibilities toward the safety of participants and the safety of a study intervention under clinical investigation are met.

The sponsor has a legal responsibility to notify both the local regulatory authority and other regulatory agencies about the safety of a study intervention under clinical investigation. The sponsor will comply with country-specific regulatory requirements relating to safety reporting to the regulatory authority, IRBs/ECs, and investigators.

Investigator safety reports must be prepared for SUSARs according to local regulatory requirements and sponsor policy and forwarded to investigators as necessary.

An investigator who receives SUSARs or other specific safety information (eg, summary or listing of SAEs) from the sponsor will review and then file it along with the SRSD(s) for the study and will notify the IRB/EC, if appropriate according to local requirements.

#### **8.4.5. Environmental Exposure, Exposure During Pregnancy or Breastfeeding, and Occupational Exposure**

Environmental exposure occurs when a person not enrolled in the study as a participant receives unplanned direct contact with or exposure to the study intervention. Such exposure may or may not lead to the occurrence of an AE or SAE. Persons at risk for environmental exposure include healthcare providers, family members, and others who may be exposed. An environmental exposure may include EDP, EDB, and occupational exposure.

Any such exposures to the study intervention under study are reportable to Pfizer Safety within 24 hours of investigator awareness.

##### **8.4.5.1. Exposure During Pregnancy**

An EDP occurs if:

- A female participant is found to be pregnant while receiving or after discontinuing study intervention.
- A male participant who is receiving or has discontinued study intervention inseminates a female partner.
- A female nonparticipant is found to be pregnant while being exposed or having been exposed to study intervention because of environmental exposure. Below are examples of environmental EDP:
  - A female family member or healthcare provider reports that she is pregnant after having been exposed to the study intervention by inhalation or skin contact.
  - A male family member or healthcare provider who has been exposed to the study intervention by inhalation or skin contact then inseminates his female partner prior to or around the time of conception.

The investigator must report EDP to Pfizer Safety within 24 hours of the investigator's awareness, irrespective of whether an SAE has occurred. The initial information submitted should include the anticipated date of delivery (see below for information related to termination of pregnancy).

- If EDP occurs in a participant/participant's partner, the investigator must report this information to Pfizer Safety via PSSA, regardless of whether an SAE has occurred. Details of the pregnancy will be collected after the start of study intervention and until 28 days after administration of the study intervention.

- If EDP occurs in the setting of environmental exposure, the investigator must report information to Pfizer Safety via PSSA. Since the exposure information does not pertain to the participant enrolled in the study, the information is not recorded on a CRF; however, a copy of the completed report is maintained in the investigator site file.
- Follow-up is conducted to obtain general information on the pregnancy and its outcome for all EDP reports with an unknown outcome. The investigator will follow the pregnancy until completion (or until pregnancy termination) and notify Pfizer Safety of the outcome as a follow-up to the initial report. In the case of a live birth, the structural integrity of the neonate can be assessed at the time of birth. In the event of a termination, the reason(s) for termination should be specified and, if clinically possible, the structural integrity of the terminated fetus should be assessed by gross visual inspection (unless preprocedure test findings are conclusive for a congenital anomaly and the findings are reported).

Abnormal pregnancy outcomes are considered SAEs. If the outcome of the pregnancy meets the criteria for an SAE (ie, ectopic pregnancy, spontaneous abortion, intrauterine fetal demise, neonatal death, or congenital anomaly), the investigator should follow the procedures for reporting SAEs. Additional information about pregnancy outcomes that are reported to Pfizer Safety as SAEs follows:

- Spontaneous abortion including miscarriage and missed abortion should be reported as an SAE;
- Neonatal deaths that occur within 1 month of birth should be reported, without regard to causality, as SAEs. In addition, infant deaths after 1 month should be reported as SAEs when the investigator assesses the infant death as related or possibly related to exposure to the study intervention.

Additional information regarding the EDP may be requested by the sponsor. Further follow-up of birth outcomes will be handled on a case-by-case basis (eg, follow-up on preterm infants to identify developmental delays). In the case of paternal exposure, the investigator will provide the participant with the Pregnant Partner Release of Information Form to deliver to his partner. The investigator must document in the source documents that the participant was given the Pregnant Partner Release of Information Form to provide to his partner.

#### **8.4.5.2. Exposure During Breastfeeding**

An EDB occurs if:

- A female participant is found to be breastfeeding while receiving or after discontinuing study intervention.

- A female nonparticipant is found to be breastfeeding while being exposed or having been exposed to study intervention (ie, environmental exposure). An example of environmental EDB is a female family member or healthcare provider who reports that she is breastfeeding after having been exposed to the study intervention by inhalation or skin contact.

The investigator must report EDB to Pfizer Safety within 24 hours of the investigator's awareness, irrespective of whether an SAE has occurred. The information must be reported via PSSA. When EDB occurs in the setting of environmental exposure, the exposure information does not pertain to the participant enrolled in the study, so the information is not recorded on a CRF. However, a copy of the completed report is maintained in the investigator site file.

An EDB report is not created when a Pfizer drug specifically approved for use in breastfeeding women (eg, vitamins) is administered in accordance with authorized use. However, if the infant experiences an SAE associated with such a drug, the SAE is reported together with the EDB.

#### **8.4.5.3. Occupational Exposure**

The investigator must report any instance of occupational exposure to Pfizer Safety within 24 hours of the investigator's awareness via PSSA, regardless of whether there is an associated SAE. Since the information about the occupational exposure does not pertain to a participant enrolled in the study, the information is not recorded on a CRF; however, a copy of the completed report is maintained in the investigator site file.

#### **8.4.6. Cardiovascular and Death Events**

Not applicable.

#### **8.4.7. Disease-Related Events and/or Disease-Related Outcomes Not Qualifying as AEs or SAEs**

Not applicable.

#### **8.4.8. Adverse Events of Special Interest**

The following events are considered AESIs:

- Confirmed diagnosis of influenza (clinical signs/symptoms and positive laboratory testing) after Day 1 through 6 months after vaccination.
- Confirmed diagnosis of myocarditis or pericarditis occurring within 28 days after vaccination. See [Section 10.11.8.10.5](#), [Section 10.12.8.10.5](#), and [Section 10.13.8.10.7](#) for additional procedures for monitoring of potential myocarditis or pericarditis.

AESIs are examined as part of routine safety data review procedures throughout the clinical trial and as part of signal detection processes. Should an aggregate analysis indicate that these prespecified events occur more frequently than expected, eg, based on epidemiological data, literature, or other data, then this will be submitted and reported in accordance with Pfizer's safety reporting requirements. Aggregate analyses of safety data will be performed on a regular basis per internal SOPs.

All AESIs must be reported as an AE or SAE following the procedures described in [Sections 8.4.1](#) through 8.4.4. An AESI is to be recorded as an AE or SAE on the CRF. In addition, an AESI that is also an SAE must be reported via PSSA.

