#### **8.4.1. Time Period and Frequency for Collecting AE and SAE Information**

The time period for actively eliciting and collecting AEs and SAEs (“active collection period”) for each participant begins from the time the participant provides informed consent, which is obtained before the participant’s participation in the study (ie, before undergoing any study-related procedure and/or receiving study intervention), through and including Visit 102 in Substudy A, Visit 202 in Substudy B, and Visit 303 in Substudy C.

Additionally, MAEs, NDCMCs, and SAEs will be collected from the time the participant provides informed consent to Visit 103 in Substudy A, Visit 203 in Substudy B, and Visit 304 in Substudy C (approximately 6 months after vaccination). In addition, AEs occurring up to 48 hours after blood draws must be recorded on the CRF.

Follow-up by the investigator continues throughout the active collection period and until the AE or SAE or its sequelae resolve or stabilize at a level acceptable to the investigator.

When a clinically important AE remains ongoing at the end of the active collection period, follow-up by the investigator continues until the AE or SAE or its sequelae resolve or stabilize at a level acceptable to the investigator and Pfizer concurs with that assessment.

For participants who are screen failures, the active collection period ends when screen failure status is determined.

If the participant withdraws from the study and also withdraws consent for the collection of future information, the active collection period ends when consent is withdrawn.

If a participant permanently discontinues or temporarily discontinues from the study because of an AE or SAE, the AE or SAE must be recorded on the CRF and the SAE reported via PSSA.

Investigators are not obligated to actively seek information on AEs or SAEs after the participant has concluded study participation. However, if the investigator learns of any SAE, including a death, at any time after a participant has concluded study participation, and they consider the event to be reasonably related to the study intervention, the investigator must promptly report the SAE to Pfizer via PSSA.

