**10.11.8.10.3. Visit 103 – 6-Month Follow-Up Visit (After Vaccination) – 175 to 189 Days After Visit 101**

- Record MAEs, SAEs, and NDCMCs as described in Section 8.4.
- Record nonstudy vaccinations as described in [Section 10.11.6.9](#).
- Record prohibited medication use as described in [Section 10.11.6.9.1](#).
- Collect a blood sample of approximately 30 mL CCI
- Complete the source documents.
- The investigator or an authorized designee completes the CRFs.
- Record any AEs that occur within the 48 hours after the blood draw as described in Section 8.4.

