3.1.3. Adverse Events

The time period for actively eliciting and collecting AEs (“active collection period”) for each participant begins from the time the participant provides informed consent, which is obtained before the participant’s participation in the study (ie, before undergoing any study-related procedure and/or receiving study intervention), through and including Visit 102 in Substudy A (approximately 4 weeks after vaccination).

Additionally, MAEs, NDCMCs, and SAEs will be collected from the time the participant provides informed consent to Visit 103 in Substudy A (approximately 6 months after vaccination). In addition, AEs occurring up to 48 hours after blood draws must be recorded on the CRF.

Standard algorithms for handling missing AE dates and missing AE severity will be applied as described in the Pfizer data standard rules.

The following derivations will be included for each participant:

- Any AE reported.
- Any related AE reported.
- Any immediate AE (assess acute reactions for at least 30 minutes after study intervention administration).
- Any SAE.
- Any MAE (an MAE is defined as a nonserious AE that results in an evaluation at a medical facility).
- Any NDCMC (an NDCMC is defined as a disease or medical condition, not previously identified, that is expected to be persistent or otherwise long-lasting in its effects [eg, asthma]).
- Any severe AE.
- Any life-threatening AE.
- Any AE leading to study withdrawal.
- Any AE leading to death.
- Any AESI.
 - Confirmed diagnosis of influenza (clinical signs/symptoms and positive laboratory testing) after Day 1 through 6 months after vaccination.
 - Confirmed diagnosis of myocarditis or pericarditis occurring within 28 days after vaccination.

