6.1.2.2. Sensitivity/Supplementary Analyses

To support the assessment of AEs, the endpoints below as specified in [Section 3.1.3](#) will be summarized with the same analysis population using the same presentation as specified in the main analysis:

- Immediate AEs

- Related AEs
- Severe AEs
- Life-threatening AEs
- AEs leading to study discontinuation/withdrawal
- AEs leading to death
- AESIs

All AEs/SAEs occurring after informed consent and prior to vaccination will not be included in the analyses but will be listed.

In addition, any AEs occurring up to 48 hours after blood draws will be listed.

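### Confirmed influenza is an AESI through 6 months, but after the 4-week visit nonserious cases not seen at a medical facility are not actively elicited

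*Protocol*

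**What the plan says.** Protocol Section 8.4.8 lists two AESIs. One is a confirmed diagnosis of influenza, requiring both clinical signs or symptoms and a positive laboratory test, with a window running "after Day 1 through 6 months after vaccination". On reporting it says "All AESIs must be reported as an AE or SAE following the procedures described in" Sections 8.4.1 through 8.4.4, and adds "An AESI is to be recorded as an AE or SAE on the CRF".

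Section 8.4.1 sets the active collection period for AEs as running "through and including Visit 102 in Substudy A, Visit 202 in Substudy B, and Visit 303 in Substudy C", which are the 4-week visits. For the longer period it says "MAEs, NDCMCs, and SAEs will be collected from the time the participant provides informed consent to Visit 103 in Substudy A", with the matching visits for Substudies B and C, and it adds AEs within 48 hours of a blood draw. AESIs are not named there. The AE-collection footnotes to the three schedules of activities repeat these limits. The 6-month visit procedure for Substudy A reads "Record MAEs, SAEs, and NDCMCs as described in Section 8.4", and the procedures for Visits 203 and 304 are worded alike.

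In the SAP for each substudy, Section 3.1.3 derives "Confirmed diagnosis of influenza (clinical signs/symptoms and positive laboratory testing) after Day 1 through 6 months after vaccination". Section 6.1.2.2 includes AESIs among the endpoints to be "summarized with the same analysis population using the same presentation as specified in the main analysis".

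**The concern.** The window of the influenza AESI and the window in which sites ask about ordinary AEs differ by about five months. Section 10.3.6 defines an MAE as a nonserious AE that leads to evaluation at a medical facility. A nonserious confirmed influenza case without such an evaluation is not an MAE or an SAE, and would not ordinarily be a new chronic condition. After week 4 it belongs to no class that the visit procedures ask about.

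The count matters for two reasons. Section 2.7.1 names breakthrough influenza as a participant risk, in a study that bars nonstudy influenza vaccine. Section 8.4.8 also provides for comparing AESI frequency with what would be expected from epidemiological or other data. A numerator that is incompletely elicited makes an excess harder to see in that comparison.

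**Working it through.** The plan states no figure for influenza incidence or its ascertainment, so there is none to reproduce. The check sets the passages side by side, then measures the length of the gap.

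**Which cases are elicited after week 4**

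| Confirmed influenza case, onset after the 4-week visit | Class elicited to 6 months | Rule that still applies |
|---|---|---|
| Serious | SAE | Sections 8.4.1 and 8.4.8 |
| Nonserious, evaluated at a medical facility | MAE | Sections 8.4.1 and 8.4.8 |
| Nonserious, not so evaluated, within 48 hours of a draw | AE after blood draw | Section 8.4.1 |
| Nonserious, not so evaluated, at other times | None | Section 8.4.8: record if the site learns of it |

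Only the last row is exposed. The 48-hour exception narrows it little: the draws concerned are at the 4-week visit and at the 6-month visit, which closes the window.

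Nothing else in the text shown prompts a report of such a case:
- No visit is scheduled between week 4 and month 6.
- At the 4-week visit participants are asked to contact the site about medically attended events or hospitalization, not about influenza.
- Myocarditis and pericarditis have a dedicated monitoring section in each substudy; influenza has none.

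**Length of the gap**

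Inputs, from the schedules of activities: 4-week visit at 28 to 35 days, 6-month visit at 175 to 189 days.

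Share of window after all-AE collection ends = (6-month day − 4-week day) / 6-month day

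- Shortest: (175 − 35) / 175 = 140 / 175 = 80.0%
- Longest: (189 − 28) / 189 = 161 / 189 = 85.2%

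**What this implies for the count**

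Let *s* be the time share above and *u* the proportion of confirmed cases that are nonserious and not evaluated at a medical facility. If the hazard were constant over the window and no exposed case were ever recorded, the fraction of AESI cases missed would be *s* × *u*. The documents give no value for *u*, so the following are assumed values to show scale only:

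| Assumed *u* | *s* = 0.80 | *s* = 0.852 |
|---|---|---|
| 0 | 0% | 0% |
| 0.10 | 8.0% | 8.5% |
| 0.25 | 20.0% | 21.3% |

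Neither condition is secure. Section 2.7.1 says the study runs mainly outside peak circulation, so the hazard need not be constant. Section 8.4.8 requires recording of any case that becomes known, so the loss would be below *s* × *u* to the extent that cases reach the site unprompted. The table is not an estimate of the undercount.

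**The case against.** The strongest reply is that Section 8.4.8 is a specific and mandatory rule with its own 6-month window. It requires every AESI to go on the CRF, with no restriction to serious or medically attended events. Section 8.4.1.2 also has investigators record spontaneously reported AEs, and Section 8.4.8.1 asks for reporting of signs, symptoms or sequelae arising from lack of efficacy. This stands against any inference that every such case is lost: a case the site learns of must be recorded. It does not supply a question at the 6-month visit, and Section 8.4.8 itself sends AESIs through Section 8.4.1, whose 6-month list omits them.

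Second, the definition needs a positive laboratory test, so many qualifying cases will involve a medical facility and be collected as MAEs. This stands and limits the size. The documents do not say where testing takes place, so it does not close the gap.

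Third, the AESI summary is supplementary and descriptive. No hypothesis or sample size depends on it. Participants and safety assessors are blinded, so there is no evident reason for ascertainment to differ between groups. This stands; the issue is the level of the count, not bias in a between-group comparison.

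Fourth, the CRF and its completion guidance are not among the documents, and an influenza prompt may already exist there. That cannot be ruled out, but the protocol would still need to match it.

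**Conclusion.** The mismatch is real and narrow. After week 4 the collection text does not elicit nonserious confirmed influenza without a medical-facility evaluation, while the SAP counts influenza AESIs to 6 months. The count may be too low by an amount that the documents do not allow one to calculate and that may be small. The conclusion assumes that sites follow the visit procedures as written and that no CRF prompt outside the documents covers the AESI.

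Three further inferences are tempting and should not be drawn:
- The 80% to 85% does not mean that AEs go uncollected for that time. MAEs, SAEs and NDCMCs are collected throughout.
- The AESI count is not the only place where influenza would appear. Cases recorded as MAEs or SAEs also enter those 6-month summaries, and the SAP presents events by system organ class and preferred term.
- The SAP does not leave the AESI window undefined. Section 6.1.2.1 omits AESIs from its timing line, but Section 6.1.2.2 refers to Section 3.1.3, which states both windows: influenza through 6 months, myocarditis or pericarditis within 28 days.

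No sample-size or precision figure in the plan changes.

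**What to change.** Reconcile the passages by adding AESIs (confirmed influenza) to the events collected through Visits 103, 203 and 304. The places to change are:
- Section 8.4.1;
- the AE-collection footnote in each of the three schedules of activities;
- the 6-month visit procedures in Sections 10.11.8.10.3, 10.12.8.10.3 and 10.13.8.10.5.

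Repeating the two AESI windows in SAP Section 6.1.2.2 would help a programmer but is optional.

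The cost is one question and one CRF line at a visit that already takes place, with no new visit, sample or test. Recall over about five months will be imperfect, so the question reduces the gap without removing it.
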